## **6.3 Discontinuation of study medication by subjects and withdrawal criteria**

### **6.3.1 Discontinuation and withdrawal - amended**

An excessive rate of patient discontinuations from either treatment or "dropouts" from the study may render the trial uninterpretable. In this trial, ascertainment of study efficacy outcome events, bleeding events, and vital status data are crucial to the primary analysis and must be collected until the end of the study, even if patients are no longer taking study medication. **Therefore, all efforts must be taken to engage patients to comply with all study procedures and to continue to be followed until the end of the trial.** Additionally, study medication compliance will be assessed as defined in Section 7.7.

Patients must be withdrawn from study drug, if any of the following occurs:

- at their own request or at the request of their legally acceptable representative. At any time during the study and without giving reasons (even though providing a reason is encouraged), a patient may decline to participate further. The patient will not suffer any disadvantage as a result,
- pregnancy,

Patients may be withdrawn from study drug, if any of the following occurs:

- if, in the investigator's opinion, continuation of the study drug would be harmful to the patient's well-being (e.g. significant decline in cognitive function or renal failure with eGFR<15 mL/min/1.73 m^2),
- at the specific request of the sponsor and in liaison with the investigator (e.g., safety concerns).

Depending on the time point of withdrawal, a withdrawn patient is referred to as either "screening failure" or "dropout" as specified below:

**Screening failure:** a patient who, for any reason (e.g., failure to satisfy the selection criteria), terminates the study before randomization.

**Dropout:** a patient who discontinues study participation prematurely for any reason, if the patient has already been randomized.

 Exclusion criterion 23 revised with Protocol Amendment 4 (change no. 17)

 Exclusion criterion 25 added with Protocol Amendment 4 (change no. 18)

 Sentence was added with Protocol Amendment 4 (change no. 16).

Reasons for discontinuing study medication should be solicited and documented. **Study medication or study ASA will not be routinely discontinued in patients reaching a potential primary efficacy event unless there is a safety concern or a clear indication for an alternative antithrombotic therapy, as determined by the local investigator.**

If study medication and/or study ASA will be temporarily interrupted or permanently discontinued, the investigator will document the reason on the electronic case report form (eCRF), and if applicable in the patient's medical records/source documents. The study medication and/or study ASA will be restarted as soon as medically justified (in the opinion of the investigator). There is no defined maximum limit for temporary treatment interruption, however, the date of temporary treatment discontinuation, date of re-starting treatment and the reason for temporary discontinuation will be documented in the eCRF.

**All patients who permanently discontinue study medication and/or study ASA and have not withdrawn consent will remain in the study, and are expected to complete all on-site study visits as originally scheduled.** If a patient permanently discontinues study medication and is unwilling or unable to attend regular study visits at the study site, the investigator and patient must determine which of the follow-up options the patient is able and willing to comply with. The patient will be approached to provide consent for further follow-up at the time of withdrawal. Options for follow-up of these patients are listed below, in descending order of preference:

1. Patient will be contacted by phone at the regular study visit intervals.
2. Patient allows his/her general practitioner (with a signed release of medical information) or a family relative to be contacted (if allowed in respective country) at the regular study visit intervals.
3. Patient will be contacted once at the end of the study.
4. No further contact.

For patients who withdraw consent for any kind of follow-up, the patient's vital status will be obtained at study end through applicable information sources according to local guidelines and as allowed by local regulations. In all cases, the reason for withdrawal must be recorded in the eCRF and in the patient's medical records.

If a patient fails to return for a study visit or is suspected to be lost to follow-up, the investigator should explore all possible options to contact the patient. The investigator should ask the patient at the time of enrollment for the contact details of an alternate contact (e.g., relative or friend) in case the patient cannot be reached. The site must document all attempts to try to contact the patient and alternate contact in the medical records/source documents. If all attempts fail (depending on local legislation), publically available information such as death registries or other registries may be accessed or private investigation to locate a patient may be initiated.

Any patient removed from the trial will remain under medical supervision until discharge or transfer is medically acceptable.

### **6.3.2 Replacement**

No patient replacements are permitted in this study.

## 6.4 Subject identification

Each patient will be allocated a unique patient identification number after informed consent is obtained, and an additional randomization number will be assigned by IxRS at the time of randomization. This randomization number will allow subsequent identification of treatment allocation.

The patient number is a 9 digit number consisting of:

- Digits 1 to 2 = Country code
- Digits 3 to 5 = Center number within the country
- (Digits 1 to 5 = Trial unit)
- Digits 6 to 9 = Current patient number within the center

## 7. Treatments

### 7.1 Treatments to be administered - amended

Study treatment assignment will be double-blind. Study treatment consists of study medication (rivaroxaban or matching placebo) in addition to study ASA, which is also dispensed by the study. Eligible study patients will be randomized in a ratio of 1:1 to one of the 2 following treatment arms:

#### Rivaroxaban group:

Rivaroxaban 2.5 mg bid (5 mg/day, immediate-release film-coated tablets for oral administration)  
+  
*ASA 100 mg od (enteric coated tablets for oral administration)*

#### Reference group:

Rivaroxaban-matching placebo bid (tablets for oral administration)  
+  
*ASA 100 mg od (enteric coated tablets for oral administration)*

In either treatment group, post-procedural concomitant treatment with clopidogrel will be allowed as described in section 8.1.

The estimated mean treatment duration will be 30 months (maximum treatment duration 42 months) in either treatment arm.

### 7.2 Identity of study treatment

Study medication and study ASA will be labeled according to the requirements of local law and legislation. Label text will be approved according to the Sponsor's agreed procedures, and a copy of the labels will be made available to the study site upon request.

 Text revised with Protocol Amendment 4 (change no. 17)

For all study medication and study ASA, a system of numbering in accordance with all requirements of Good Manufacturing Practice (GMP) will be used, ensuring that each dose of study medication and study ASA can be traced back to the respective bulk batch of the ingredients. Lists linking all numbering levels will be maintained by the Sponsor's Quality Assurance group.

A complete record of batch numbers and expiry dates of all study medication and study ASA as well as the labels will be maintained in the Sponsor's study file.

### **7.3 Treatment assignment - amended**

Allocation to treatment arms will be done centrally by IxRS. Allocation will be performed in a ratio of 1:1 to each study treatment arm and will be stratified in one of 3 strata by:

- surgical revascularization,
- endovascular revascularization with clopidogrel,
- endovascular revascularization without clopidogrel.

Given potential differences in natural history resulting from procedure type, variation in medical practice, and concomitant therapy that may affect treatment outcome.

The clopidogrel use defining the randomization strata refers to actual clopidogrel use, at randomization, as adjunct treatment for the qualifying revascularization. Specific procedures for treatment assignment through the IxRS will be described in the IxRS manual.

### **7.4 Dosage and administration - amended**

Patients will be provided with high-density polyethylene (HDPE) bottles containing immediate-release film-coated tablets of study medication rivaroxaban 2.5 mg (or matching placebo) and HDPE bottles containing enteric-coated tablets of study ASA 100 mg. The dose amount distributed per on-site visit will be sufficient to cover a period of between the study visits at the investigational site.

All study medication treatments will be taken orally. Study medication (rivaroxaban or placebo) will be taken twice daily (generally in the morning and in the evening, approximately 12 hours apart) and study ASA will be taken once daily, generally in the morning.

If a dose of study medication is missed and less than 6 hours have elapsed since the time that the missed dose was due, it should be taken immediately. If more than 6 hours have elapsed since the missed dose was due, the dose should be skipped and the next dose of study rivaroxaban or placebo should be taken according to schedule. A missed dose from a previous calendar day should not be taken with the current dose.

For patients using a parenteral anticoagulant, the timing of the first dose of study medication administration should be no sooner than: 2 hours after final dose bivalirudin, 4 hours after final dose of intravenous unfractionated heparin, eptifibatide, or tirofiban, 12 hours after final

---

 Text modified via Protocol Amendment 5 (change no. 7)

dose of other intravenous or subcutaneous anticoagulants (e.g., enoxaparin, dalteparin) and 24 hours after final dose of abciximab or fondaparinux. Depending on the patient and the clinical setting, initiation of study medication in a patient with low risk of bleeding, who is on low dose subcutaneous anticoagulants sooner than 12 hours may be appropriate and permissible (consult Study Helpline).

Clopidogrel (at a dose that is consistent with the site/country's standard of care) may be used at the discretion of the investigator, as described in Section 8.1.

#### **7.4.1 Dose modifications**

The investigator should interrupt study medication and/or study ASA for a given patient if continuation is deemed to be detrimental to the patient's well-being. All patients who interrupt study medication and/or study ASA should resume treatment when possible. If there is concern that the patient may be intolerant of study treatments or if the patient is reluctant to take the full dose of study medication, a possible approach to restarting study medications is to reduce the frequency of dosing to once-daily or alternate-daily.

Irrespective of whether or not treatment is resumed, all patients must be followed according to the study protocol until the end of the study. Permanent study drug discontinuation should be recorded on the eCRF, giving the date and primary reason for stopping the study medication and/or study ASA. If one of the study treatments needs to be interrupted, other study treatments should be continued. For example, if study medication is interrupted, study ASA should be continued.

This section provides a general guide for investigators on the management of patients who develop intercurrent illnesses or bleeding during the course of the study. The guidance provided in this section does not replace clinical judgment nor usual care in determining the appropriate management strategy for individual patients.

The following sections provide general guidance for use of rivaroxaban. For use of ASA, please refer to applicable guidelines and local production information.

#### **7.4.2 Guidance for the treatment of subjects who require an invasive procedure**

If a patient requires an invasive procedure that is associated with a standard or high risk of bleeding (i.e., any procedure that is not considered "minor"), study medication must be interrupted.

##### **Dosing recommendations before and after invasive procedures and surgical intervention**

If an invasive procedure or surgical intervention is required, study medication should be stopped **at least 12 hours** before the intervention, if possible and based on the clinical judgment of the physician. If the procedure cannot be delayed, the increased risk of bleeding should be assessed against the urgency of the intervention. Study medication should be restarted after the invasive procedure or surgical intervention as soon as possible, provided the clinical situation allows and adequate hemostasis has been established.

 Text revised with Protocol Amendment 4 (change no. 17)

#### **7.4.3 Guidance for the treatment of subjects who require coronary artery bypass graft (CABG) surgery – amended**

Patients who are scheduled for CABG surgery during the course of the trial, ideally should interrupt study medication at least 12 hours before coronary artery bypass graft surgery in order to minimize the risk of bleeding.

Study medication may be interrupted and/or non-study ASA may be used at the discretion of the investigator. The timing of resumption of study medication after surgery is at the discretion of the investigator but, in general, study medication or study ASA should be resumed once the chest tubes are removed and hemostasis is assured. Study medication should be interrupted if patients require systemic anticoagulation. In all cases, the goal should be to resume study medication as soon as it is clinically warranted prior to being discharged from the hospital.

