### Discontinuation of Study Drug for a Vascular Procedure

**Table 8–1** depicts the approximate equivalent dose of subcutaneous enoxaparin (mg/kg) relative to rivaroxaban 2.5 mg at given time points following its administration, and should be used to assist the investigator in deciding which dose of enoxaparin or equivalent dose of another antithrombotic agent to administer in the event when a patient may have to undergo an emergency interventional coronary procedure or pharmacologic reperfusion while receiving study drug.

**Table 8–1: Comparative antithrombotic effect at given time points following rivaroxaban 2.5 mg administration to subcutaneous enoxaparin doses**

Time after 2.5 mg Rivaroxaban Administration	Equivalent Enoxaparin Dose
3 h	0.15 mg/kg
6 h	0.1 mg/kg
> 9 h	0 mg/kg

Source: [Mega et al. 2012]

When thrombolysis is required within 3 hours of the last study drug administration, it may be necessary to unblind the patient at the discretion of the investigator to estimate the dose of enoxaparin to be administered; in the case the patient is in the rivaroxaban treatment group, the subcutaneous dose of enoxaparin should be adopted as given in **Table 8–1**.

In case of urgent PCI for acute ischemic event, the investigator should discontinue study medication and initiate therapy with non-study ASA prior to PCI with non-enteric coated formulation. The loading dose of non-study ASA may be considered. In addition, consider intravenous administration of 0.5 mg/kg of enoxaparin or its antithrombotic equivalent in patients who undergo PCI. In the event that a patient requires a non-emergency revascularization procedure (PCI or CABG), study medication should be stopped approximately 24 hours before the procedure, if possible, and appropriate anticoagulant or antiplatelet therapy should be instituted as medically indicated (including DAPT).

 Depending on the bleeding risk, the patient may, at the discretion of the managing physician, resume study medication thereafter, but no earlier than approximately 12 hours after the arterial sheath has been removed (for patients undergoing PCI) or after the post-procedural drains have been removed (for patients undergoing CABG surgery), and the last dose of parenteral anticoagulant therapy has been administered.

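### Protocol 7.4.2/7.4.3 and 8.1 give different times for stopping study medication before planned CABG or PCI, and their restart wording is not aligned

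*Protocol*

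**What the plan says.** Four places in the protocol bear on stopping study medication before a planned coronary procedure and restarting it afterwards.

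- **7.4.2 (invasive procedures in general).** Study medication should be stopped "at least 12 hours before the intervention, if possible and based on the clinical judgment of the physician". It should restart as soon as the clinical situation and hemostasis allow.
- **7.4.3 (CABG).** Scheduled patients "ideally should interrupt study medication at least 12 hours before coronary artery bypass graft surgery". Restart timing is left to the investigator, with this given as the usual point: "study medication or study ASA should be resumed once the chest tubes are removed and hemostasis is assured". The section also asks for interruption when systemic anticoagulation is needed.
- **7.4.4 (acute coronary syndrome, and PCI with stenting).** It calls for temporary interruption but gives no number of hours before the procedure. Restart is left to the physician and investigator, with no earliest time.
- **8.1, under Discontinuation of Study Drug for a Vascular Procedure.** For non-emergency PCI or CABG, "study medication should be stopped approximately 24 hours before the procedure, if possible". Restart is at the managing physician's discretion. The earliest point is given as "no earlier than approximately 12 hours after the arterial sheath has been removed (for patients undergoing PCI) or after the post-procedural drains have been removed", the latter for CABG, and once the last parenteral anticoagulant dose has been given.

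7.4.1 describes the guidance in this part of the protocol as general and as no replacement for clinical judgement. 13.3 asks for strict adherence to what the protocol specifies. Neither section says whether 7.4 or 8.1 prevails where they differ.

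**The concern.** The same planned CABG is covered by 7.4.2, 7.4.3 and 8.1, and the stated stop times are not the same. Someone who looks up CABG in 7.4.3 finds 12 hours as the minimum. Someone who looks up vascular procedures in 8.1 finds about 24 hours. A monitor has no rule for deciding whether a stop at 12 hours departs from the protocol. Restart raises the same difficulty, made worse by a sentence in 8.1 whose meaning for CABG is unclear.

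The protocol itself links this instruction to safety. 7.4.3 gives reduction of bleeding risk as the reason for the pre-operative stop, 3.4 names peri-procedural bleeding as a focus of the data monitoring committee, and TIMI major bleeding is the primary safety outcome. At stake is a clear, uniform instruction to sites about a blinded anticoagulant around major procedures.

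**Working it through.** No planned statistic depends on these sections and there is no figure of the plan to reproduce. The check sets the texts side by side and asks which courses of action satisfy all of them.

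| | 7.4.2 (general) | 7.4.3 (CABG) | 7.4.4 (PCI) | 8.1 (non-emergency PCI or CABG) |
|---|---|---|---|---|
| Stop before procedure | at least 12 h, if possible | at least 12 h, ideally | no hours given | about 24 h, if possible |
| Earliest restart | as soon as possible, hemostasis established | in general, chest tubes out and hemostasis assured; investigator decides | physician and investigator decide | PCI: about 12 h after sheath removal. CABG: drains out, with or without a further 12 h. Both: last parenteral anticoagulant dose given |

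**Stop time, CABG.** The 12-hour figure is a minimum.
- Stop at about 24 h: meets 7.4.2 and 7.4.3 (24 ≥ 12) and 8.1.
- Stop at 12 h: meets 7.4.2 and 7.4.3, but not 8.1.

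Section 7.4 gives doses about 12 hours apart, so the difference is (24 − 12)/12 = 1 dose.

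**Stop time, PCI.** 7.4.4 gives no interval. The 12-hour figure applies only if PCI is taken as an invasive procedure under 7.4.2, which covers procedures that are not minor. If so, the comparison is the same as for CABG.

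**Restart, PCI.** A restart 6 hours after sheath removal, taken as an example, could fit 7.4.4 but falls short of the floor in 8.1. This mismatch does not depend on any disputed reading.

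**Restart, CABG.** The 8.1 sentence has two readings.
- The 12 hours belong to sheath removal only. Drain removal is then the trigger, which largely agrees with chest-tube removal in 7.4.3.
- The 12 hours apply to drain removal as well. 8.1 then adds about 12 hours that 7.4.3 does not mention.

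On either reading 8.1 also ties restart to the last parenteral anticoagulant dose. 7.4.3 tells sites to interrupt when systemic anticoagulation is needed, but sets no such restart condition. A restart at the later time still fits 7.4.3, which gives no deadline in hours.

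**Residual drug, for scale only.** 7.4.4 and 7.4.6 give a half-life of 5 to 13 hours. Assuming simple exponential decline, the fraction remaining is 2^(−t/half-life):
- t = 12 h: 2^(−12/5) = 0.19 to 2^(−12/13) = 0.53
- t = 24 h: 2^(−24/5) = 0.04 to 2^(−24/13) = 0.28

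The ratio between the two stop times is 2^(12/13) = 1.9 to 2^(12/5) = 5.3. Against this, Table 8-1 in 8.1 puts the enoxaparin-equivalent effect of a 2.5 mg dose at 0 mg/kg beyond 9 hours, which covers both 12 and 24 hours.

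**Event counting.** The on-treatment scope (Protocol 10.3.1, SAP 4.5.2) runs to 2 days after permanent discontinuation. A temporary stop of 12 or 24 hours does not end it, so the same bleeding events are counted whichever section a site follows.

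**The case against.** The strongest reply is that the sections are compatible. A minimum of 12 hours is met by stopping at about 24, and a late restart breaches nothing in 7.4. The wording is flexible throughout, and 7.4.1 defers to clinical judgement. This reply stands against one inference a reader might draw, that a site cannot comply with both sections: it can. It does not remove the point that a site relying on 7.4.2 or 7.4.3 alone may stop later than 8.1 asks.

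Three other inferences are tempting and are not supported.

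- **That restart after CABG differs by 12 hours.** This holds on only one of the two readings of the 8.1 sentence.
- **That 8.1 sends readers to 7.4.3 and 7.4.4 for stop times and then contradicts them.** The cross-reference in 8.1 sits in a bullet about non-study ASA and most naturally concerns ASA. It is weak evidence about timing.
- **That a roughly two- to five-fold difference in residual drug means more bleeding.** The documents do not connect the two, and Table 8-1 points the other way.

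It can also be said that treatment is blinded and randomization is balanced within country and stratum, so a site's habit applies to patients in both arms. That is a fair answer to any suggestion of differential management. Stop timing changes active-drug exposure only in the rivaroxaban arm, but the documents give no expected number of planned CABG or PCI procedures, so no effect on the bleeding comparison can be calculated.

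**Conclusion.** The inconsistency is real and modest. For non-emergency CABG the stop times in 7.4.2/7.4.3 and in 8.1 differ by about one dose. For non-emergency PCI the same is true if 7.4.2 is taken to cover it. Restart after PCI has a floor in 8.1 and none in 7.4.4. Restart after CABG is ambiguous in 8.1 and carries an extra anticoagulant condition there. Nothing in the protocol states which text governs.

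The one-dose figure rests on dosing about 12 hours apart and on a site stopping at the 12-hour minimum. The consequence for bleeding cannot be quantified from the documents. Alpha, power, the event target and the counting of events are unaffected. This is a clarification of safety instructions worth making because it is specific and cheap. It is not a defect that threatens the trial's conclusions. No view is taken here on which timing is right.

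**What to change.** Reconcile 7.4.2, 7.4.3, 7.4.4 and 8.1. State one pre-procedure interval for non-emergency CABG and PCI in one place, together with one restart condition for each procedure. Word the restart condition so that it is clear whether any number of hours applies after drain removal and how the last parenteral anticoagulant dose enters. Replace the other texts with a cross-reference. The sponsor's clinical team must decide which interval and which restart condition stand.

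The cost is protocol wording, in a clarification memo or the next amendment, and a notice to sites. It needs no extra patients or procedures and no change to the SAP.
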